Safety analysis for Months 1-12 and Months 13-48 of the treatment period will be specified in the statistical analysis plan. No statistical tests will be performed to evaluate potential differences between dose groups following the 12-month placebo-controlled portion of the 48-month Treatment Period. Safety data from subjects randomized to the elagolix 200 mg BID alone treatment group will be summarized separately from subjects randomized to the elagolix 200 mg BID plus E2/NETA (1 mg/0.5 mg) QD arm.

Other safety analyses will be pre-specified in the SAP.

Pharmacokinetic:

Exposures of elagolix and norethindrone will be summarized and elagolix concentrations may be used to develop a population pharmacokinetic model. Additional parameters may be calculated if useful for the interpretation of the data.

Pharmacodynamic:

Concentrations of estradiol (E2) will be obtained throughout the Treatment Period. Additional pharmacodynamic parameters may be calculated if useful in the interpretation of the data.

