Study drug kits will be dispensed to subjects at each on-site visit with the exception of the final visit at Treatment Month 48. Subjects randomized to elagolix plus E2/NETA on Day 1 of the Treatment Period will continue with the same dosing regimen (dose and frequency) throughout the entire Treatment Period; subjects randomized to elagolix 200 mg BID alone during the first 6 months will be reassigned to receive elagolix 200 mg BID plus E2/NETA (1 mg/0.5 mg) QD for the remainder of the Treatment Period (Months 7 – 48); subjects randomized to placebo will be reassigned at Treatment Month 12 to receive elagolix 200 mg BID plus E2/NETA (1 mg/0.5 mg) QD for the remainder of the Treatment Period. All subjects will know they are receiving elagolix 200 mg BID plus E2/NETA (1 mg/0.5 mg) QD during Months 13 – 48.

Through Treatment Month 12, subjects will use the daily e-Diary to continue recording:

- endometriosis-associated pain (DYS and NMPP via the 4 point Endometriosis Daily Pain Impact Scale) (no pain, mild pain, moderate pain, severe pain coded as 0 – 3)
- dyspareunia via a 4-point scale (no pain, mild pain, moderate pain, severe pain coded as 0-3, and not applicable)
- the presence of uterine bleeding (menstrual period and other uterine bleeding) and intensity of bleeding (spotting, light, medium, heavy)
- use of protocol specific analgesic rescue medications for endometriosisassociated pain

[figure not shown]
At the Day 1 visit (prior to dosing) and at all monthly visits during the Treatment Period (on-site and phone contacts), site staff will administer to subjects the overall endometriosis-associated pain questionnaire, an 11-point numeric rating scale (NRS).

Information regarding the use of rescue analgesic medications for endometriosisassociated pain will be collected at monthly study visits and recorded in source documents and eCRF.

At select study visits, subjects will be asked to complete various patient-reported outcome (PRO) questionnaires, including a Patient Global Impression of Change (PGIC). Vital signs assessments will be conducted at designated time points. Additional safety assessments including mammograms, TVUs, Pap tests, endometrial biopsies, and DXAs are completed as appropriate throughout the Treatment Period.

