5.5.3 Method of Assigning Subjects to Treatment Groups

All subjects will be centrally randomized using an IRT. Before the study is initiated, contact information and user guidelines for IRT will be provided to each site. Study drug will be dispensed at the study visits outlined in Appendix C, Study Activities.

As subjects enter into either the Washout Period or the Screening Period, a unique subject number will be assigned to each subject by IRT. This unique subject number will be used for each subject throughout the study.

After confirming that the subject has met randomization criteria and prior to the Day 1 (randomization) dose, a unique randomization number will be provided via IRT.

Subjects will be randomly assigned by IRT to one of the treatment groups as outlined in Section 5.5.1 upon entry into the Treatment Period.

For the second 6 months of the Treatment Period (Months 7 – 12), subjects previously randomized to elagolix 200 mg BID alone will be re-assigned by IRT to the elagolix 200 mg BID plus E2/NETA (1 mg/0.5 mg) QD treatment group as outlined in Section 5.5.1. At Treatment Month 12, all subjects will be re-assigned by IRT to receive open label elagolix 200 mg BID plus E2/NETA (1 mg/0.5 mg) QD, including subjects previously randomized to placebo. Subjects re-assigned by IRT will not be assigned new subject numbers.

In the event a study drug kit becomes lost or damaged, the site can contact IRT to obtain an unscheduled study drug kit re-supply to dispense to the subject. Sites will register subjects as "Completed" or "Discontinued" (if the subject prematurely discontinues) at the end of the Treatment Period and will also indicate whether the subject will enter the Follow-Up Period.

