8.1.1 General Considerations

The SAS system will be used to perform the statistical analyses. All statistical tests will be two-sided and a significance level of 0.05 will be used unless otherwise specified. A test will be deemed statistically significant if the *P* value rounded to three decimal places is less than or equal to 0.050 unless otherwise specified. The primary safety and efficacy comparisons will be between the elagolix plus E2/NETA treatment group and the placebo group. Data from subjects randomized to elagolix 200 mg BID alone will be summarized separately from subjects randomized to the elagolix 200 mg BID plus E2/NETA (1 mg/0.5 mg) QD arm. Unless otherwise specified, no statistical tests will be performed to evaluate potential differences between the two elagolix dose groups.

Data collected during the treatment period will be summarized by randomized treatment assignment on study Day 1.

- Subjects randomized to elagolix plus E2/NETA in the first 12 months of treatment.
- Subjects randomized to elagolix alone in the first 6 months of treatment
- Subjects randomized to placebo in the first 12 months of treatment

Analysis details will be specified in the statistical analysis plan. No statistical tests will be performed to evaluate potential differences between dose groups following the 12 month placebo-controlled portion of the 48-month Treatment Period.

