8.1.7.4 Bone Mineral Density

The key BMD assessment comparisons are at the lumbar spine at Month 6 and Month 12. Secondary BMD endpoints include total hip and femoral neck. The elagolix 200 mg BID plus E2/NETA (1 mg/0.5 mg) QD dose will be compared to placebo at Months 6 and 12 and will be compared to Elagolix 200 BID alone at Month 6 based on percent change from baseline.

Percent change from baseline in BMD during Months 13 through 48, as well as Z-score and T-score values will also be summarized.

Full analysis details will be provided in the SAP.

Post-treatment bone mineral density scans will be summarized similarly, as appropriate. Percentage change from baseline in the post-treatment period will be compared with the percentage change from baseline at the end of the treatment period. There will be no statistical testing in the Follow-Up period.

Additional analysis details will be specified in the SAP.

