9.0 Safety Analyses

9.1 General Considerations

Safety summaries will be provided separately using the Safety Analysis Set during the placebo-controlled Treatment Period, Safety Analysis Set during the open-label Treatment

Period, and All Elagolix plus E2/NETA Analysis Set as defined in Section 4.0. Unless otherwise specified, no statistical comparisons or tests will be performed on Safety Analysis Set during the open-label Treatment Period or the All Elagolix plus E2/NETA Analysis Set.

Unless otherwise specified, the baseline for the 12-month placebo-controlled Treatment Period will be the last non-missing value obtained prior to or on Study Day 1. The baseline during the open-label Treatment Period will be the last non-missing value obtained prior to or on the initiation day of elagolix (either elagolix alone or elagolix plus E2/NETA). The baseline for All Elagolix plus E2/NETA Analysis Set will be the last non-missing value obtained prior to or on the initiation day of elagolix plus E2/NETA.

All safety analyses will be based on observed data. Unless otherwise specified, missing data will not be imputed.

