9.5.2.1 Bone Mineral Density during the Treatment Period

BMD

A summary of continuous BMD at each scheduled assessment will be provided during the appropriate Treatment Period. This summary will include the sample size, mean, SD, median, minimum, and maximum. This analysis will be repeated including subjects who switch machine manufacturer type (Lunar or Hologic), for subjects with scans only on Lunar machines, and for subjects with scans only on Hologic machines.

The analysis of percent change in BMD from baseline to each relevant visit during the Treatment Period will be based on an ANCOVA model with treatment as the main effect and baseline value of corresponding parameter as a covariate. Elagolix plus E2/NETA group will be compared to placebo at Months 6 and 12 and will be compared to the

elagolix alone group at Month 6 during the placebo-controlled Treatment Period. In addition, elagolix alone group will be compared to placebo at Months 6 and 12 during the placebo-controlled Treatment Period. This analysis will be repeated including subjects who switch machine manufacturer type (Lunar or Hologic), for subjects with scans only on Lunar machines, and for subjects with scans only on Hologic machines.

The number and percentage of subjects with percent change from Baseline to each scheduled assessment during the Treatment Period in mutually exclusive categories of BMD decrease: $\leq 0\%$, $> 0\% - \leq 1.5\%$, $> 1.5\% - \leq 3\%$, $> 3\% - \leq 4\%$, $> 4\% - \leq 5\%$, $> 5\% - < 8\%$, and $\geq 8\%$ will be summarized by treatment group. Elagolix plus E2/NETA group will be compared to placebo at Months 6 and 12 and will be compared to elagolix alone group at Month 6 during the placebo-controlled Treatment Period using chi-square tests. In addition, elagolix alone group will be compared to placebo at Months 6 and 12 during the placebo-controlled Treatment Period.

The analysis of percent change in BMD from Month 6 to Month 12 during the Treatment Period will be based on an ANCOVA model with treatment as the main effect and Month 6 BMD values of corresponding parameter as a covariate for subjects who have both Month 6 and Month 12 BMD values. Same analyses will be provided for percent change in BMD from Month 6 to Month 18 and Month 24. Each elagolix group will be compared to placebo.

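### SAP 9.5.2.1 compares BMD change from Month 6 to Months 18 and 24 with a placebo arm that takes elagolix plus E2/NETA from Month 12

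*SAP*

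**What the plan says.** SAP 9.5.2.1 has a paragraph on BMD change measured from Month 6. It uses an ANCOVA with treatment as main effect and Month 6 BMD as covariate for the change to Month 12, in subjects with both scans. It then says "Same analyses will be provided for percent change in BMD from Month 6 to Month 18 and Month 24" and closes with "Each elagolix group will be compared to placebo".

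The protocol moves the comparator arm onto active drug at the end of the double-blind year. Section 5.1 says "subjects randomized to placebo will be reassigned at Treatment Month 12 to receive elagolix 200 mg BID plus E2/NETA", and Section 5.5.3 says "At Treatment Month 12, all subjects will be re-assigned by IRT to receive open label elagolix 200 mg BID plus E2/NETA". SAP 4.0 groups safety data by treatment at randomization, so these subjects stay under the placebo heading after the switch.

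On comparisons after Month 12, the protocol synopsis (safety) states "No statistical tests will be performed to evaluate potential differences between dose groups following the 12-month placebo-controlled portion of the 48-month Treatment Period", and Section 8.1.1 repeats it: "No statistical tests will be performed to evaluate potential differences between dose groups following the 12 month placebo-controlled portion of the 48-month Treatment Period". Section 8.1.7.4 plans BMD comparisons with placebo at Months 6 and 12. For the later period it says "Percent change from baseline in BMD during Months 13 through 48, as well as Z-score and T-score values will also be summarized". SAP 9.1 adds that "no statistical comparisons or tests will be performed on Safety Analysis Set during the open-label Treatment Period", but opens that sentence with an allowance for exceptions specified elsewhere.

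**The concern.** After Month 12 there is no placebo arm. A comparison over Month 6 to 18 or Month 6 to 24 sets subjects on active drug for the whole span against subjects on placebo for six months and then on the same combination. For the elagolix plus E2/NETA arm this is continued versus delayed start. For the elagolix-alone arm it is add-back begun at Month 6 after monotherapy versus the combination begun at Month 12. Neither is a placebo comparison.

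The effect on bone relative to placebo at 6 and 12 months is a stated objective (Protocol 4.0, SAP 2.1). A Month 18 or Month 24 figure labelled as a difference from placebo would be read as an extension of that evidence to longer exposure. If bone loss on the drug is steady or front-loaded, that figure would understate it, which is the unfavourable direction for a safety endpoint.

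**Working it through.** The documents give no BMD effect size, standard deviation, power or time course, so there is no plan figure to reproduce. The check is exposure arithmetic, two illustrations under stated assumptions, and a comparison of the texts.

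**Inputs.** Spans start at Month 6 and end at Month M = 12, 18 or 24 (SAP 9.5.2.1). The placebo arm switches at Month 12 (Protocol 5.1, 5.5.3). Group labels are those at randomization (SAP 4.0).

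**1. Exposure of the former placebo arm.** Share of the span on active drug = (M − 12)/(M − 6).
- Month 6–12: 0/6 = 0%
- Month 6–18: 6/12 = 50%
- Month 6–24: 12/18 = 67%

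Only the first span is placebo-controlled throughout.

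**2. Constant slopes (assumption A).** Let BMD change by a per month on drug and p per month on placebo.
- Continuously treated combination arm: a(M − 6)
- Former placebo arm: 6p + a(M − 12)
- Contrast as specified: 6(a − p)
- Contrast with continued placebo: (M − 6)(a − p)
- Ratio: 6/(M − 6), which is 6/12 = 50% at Month 18 and 6/18 = 33% at Month 24, whatever the value of p

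**3. Loss that levels off (assumption B).** Let loss after t months on drug be A·f(t) with f(t) = 1 − exp(−t/τ), and no change on placebo. The ratio is 1 − f(M − 12)/[f(M) − f(6)]. For τ = 12 and M = 18, f(6) = 0.3935 and f(18) = 0.7769, so the ratio is 1 − 0.3935/0.3834 = −0.03.

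| τ (months) | Month 6–18 | Month 6–24 |
|---|---|---|
| 60 | 42% | 23% |
| 36 | 36% | 15% |
| 24 | 28% | 4% |
| 18 | 19% | −7% |
| 12 | −3% | −34% |

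The ratio is zero at τ of about 12.5 months (Month 6–18) and 21.3 months (Month 6–24). Below those values the contrast has the wrong sign.

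**4. A cruder model as a cross-check.** Let the first six months on drug have g times the effect of each later six-month block, with no change on placebo. The ratio is (2 − g)/2 at Month 18 and (2 − g)/3 at Month 24.
- g = 0.5: 75% and 50%
- g = 1: 50% and 33%
- g = 2: 0% and 0%
- g = 3: −50% and −33%

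Both models show the contrast can be diluted, vanish or reverse.

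The figures in steps 2 to 4 are for the combination arm. For the elagolix-alone arm, 50% and 33% hold only if its slope after add-back begins at Month 6 equals the combination slope.

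**5. The texts side by side.** The two protocol statements against tests after the placebo-controlled portion (synopsis, 8.1.1) carry no exception clause. Elsewhere the SAP does limit its comparisons. The two preceding comparison paragraphs of 9.5.2.1 confine placebo comparisons to the placebo-controlled period, 9.5.6.2 (endometrial thickness) ends them there, and 9.5.2.2 (follow-up BMD) uses an ANCOVA but rules out comparison. The sentence at issue has no such limit.

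**The case against.** The strongest reply is that the SAP permits this. The bar in SAP 9.1 yields to exceptions, and 9.5.2.1 can be read as one. The paragraph speaks of comparing and names no test or p-value, whereas the protocol bars statistical tests, and the protocol leaves analysis detail for Months 13–48 to the SAP. Because the SAP writes out a prohibition where it wants one, its absence here may be deliberate. A contrast of randomized arms after the switch can also be informative.

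Part of this stands. Within the SAP alone there is no breach, and whether a formal test is intended is unclear. But an ANCOVA with treatment as main effect, in which groups are to be compared, is a between-group comparison. Leaving detail to the SAP does not plainly license what the protocol rules out. None of this makes the comparator placebo.

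It is also fair that the percentages are hypothetical. They use assumed time courses, and they ignore both the Month 6 covariate and the restriction to subjects with both scans. They show how the contrast behaves and do not estimate its bias in this trial.

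Finally, the scope is small. The analysis lies outside the testing hierarchy in SAP 10.0, and open-label BMD summaries with a pre-elagolix baseline are already planned (SAP 9.1, 9.5.2.1).

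**Conclusion.** The concern holds. Followed as written, SAP 9.5.2.1 yields Month 6-to-18 and Month 6-to-24 comparisons labelled as against placebo, with the comparator on elagolix plus E2/NETA for 50% and 67% of the span. That rests on the documents alone, as does the departure from the protocol's BMD plan, which names placebo comparisons only at Months 6 and 12.

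The share of the placebo-referenced difference that would be seen depends on an unstated time course. It is 50% and 33% under constant slopes, less if loss is front-loaded (to the point of reversal), and more if loss accelerates. The key Month 6 and Month 12 BMD comparisons, the co-primary endpoints and type I error control are unaffected. This should be corrected, but it does not threaten the main conclusions.

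**What to change.** Limit the closing sentence of that paragraph in SAP 9.5.2.1 so that the comparison of each elagolix group with placebo applies to the Month 6-to-12 change only, and state that the Month 6-to-18 and Month 6-to-24 changes are not compared between groups. Present the two later spans by randomized group with within-group confidence intervals, and label the arm as placebo followed by elagolix plus E2/NETA. This keeps the description of the elagolix-alone arm after add-back begins. For open-label BMD in the former placebo arm, rely on the pre-elagolix baseline in SAP 9.1.

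If a between-group contrast is still wanted, call it early versus delayed start, describe the elagolix-alone version separately, and reconcile it with the protocol synopsis and Sections 8.1.1 and 8.1.7.4.

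The cost is one sentence of SAP wording, a table label and within-group intervals from data already being collected.

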9.5.2.2 Bone Mineral Density during the Follow-up Period

BMD

A summary of continuous BMD at each scheduled assessment will be provided by treatment group during the Follow-up Period. This summary will include the sample size, mean, SD, median, minimum, and maximum. This analysis will be repeated including subjects who switch machine manufacturer type (Lunar or Hologic).

The analysis of percent change in BMD from baseline to each relevant visit during the Follow-up Period will be based on an ANCOVA model with treatment as the main effect

and baseline value of corresponding parameter as a covariate. No comparison will be performed during the Follow-up Period. This analysis will be repeated including subjects who switch machine manufacturer type (Lunar or Hologic).

The analysis of percent change in BMD from baseline will be repeated for the following subset of subjects:

- subjects who have a Treatment Month X (e.g., Month 12) scan and a Follow-up Month Y (e.g., Follow-up Month 6) scan and premature discontinue prior to next scheduled assessments.

The number and percentage of subjects with percent change from Baseline to each scheduled assessment during the Follow-up Period in mutually exclusive categories of BMD decrease: $\leq 0\%$, $> 0\% - \leq 1.5\%$, $> 1.5\% - \leq 3\%$, $> 3\% - \leq 4\%$, $> 4\% - \leq 5\%$, $> 5\% - < 8\%$, and $\geq 8\%$ will be summarized by treatment group.

In addition, the number and percentage of subjects with percent change from final on-treatment to each scheduled assessment during the Follow-up Period in mutually exclusive categories of BMD decrease: $\leq 0\%$, $> 0\% - \leq 1.5\%$, $> 1.5\% - \leq 3\%$, $> 3\% - \leq 4\%$, $> 4\% - \leq 5\%$, $> 5\% - < 8\%$, and $\geq 8\%$ will be summarized by treatment group.

For the purpose of assessing post-treatment BMD recovery, the following summaries will be provided. The "recovery" statistic was defined as

Recovery at Follow-up Month X = $100 \times ((\% \text{ change from baseline to final}) - (\% \text{ change from baseline to Follow-up Month X})) / (\% \text{ change from baseline to final})$

The "recovery" statistic is the proportion of BMD decrease at the final treatment scan recovered at Follow-up Month X. For example, a subject who has a change of -2% at the end of treatment and has a change of -1% at Follow-up Month 6 has a recovery value of 50% at Follow-up Month 6. This statistic will only be defined for subjects who experienced a decrease from baseline at final treatment.

A continuous summary of recovery at each relevant visit during the Follow-up Period will be provided including mean, standard deviation, median, and a within-group 95% confidence interval for the following subset of subjects:

- All subjects who experienced a decrease from baseline at final treatment;
- Subjects who premature discontinue after Month 6 and on or prior to Month 12;
- Subjects who premature discontinue after Month 12 and on or prior to Month 18;
- Subjects who premature discontinue after Month 18 and on or prior to Month 24;
- Subjects who premature discontinue after Month 24 and on or prior to Month 30;
- Subjects who premature discontinue after Month 30 and on or prior to Month 36;
- Subjects who premature discontinue after Month 36 and on or prior to Month 42;
- Subjects who premature discontinue after Month 42 or completed the Treatment Period.

Additionally, the number and percentage of subjects in each of the following categories will be provided for the subset of subjects listed above: < 0%, 0 – 25%, > 25 – 50%, > 50 – 75%, > 75 – 100%, > 100%.

Bone loss will be defined as > 3% at the spine, > 4% at the total hip, or > 5% at the femoral neck. The following listings will be provided:

- Listing of subjects with bone loss from baseline to final on-treatment visit and have continued bone loss from final on-treatment to Follow-up visits will be provided. Subjects subsequently with an increase from Follow-up Month 6 to a subsequent Follow-up assessment will be excluded from this listing.

In addition, the following plots will be provided:

- Cumulative distribution function of recovery at Follow-up Month 6 and Follow-up Month 12.
- Percent change from baseline to treatment and follow-up months of interest.

